7.2 Secondary Efficacy Analyses

For time-to-event endpoints (e.g. DFS, OS), Kaplan-Meier / product limit method will be used to estimate the survival distributions over time, and to estimate median time to event. Where appropriate, inference for time-to-event endpoints will be assessed using the Log-rank test statistic, and the treatment effect will be estimated using Cox proportional hazards model. The assumption of proportional hazards will be assessed graphically.

The following will be analysed using Kaplan-Meier time-to-event methodology:

- Time To Recurrence, defined as the time from randomization to recurrence.
 - Recurrence is defined as disease that has recurred to the same extent of disease (ie same stage / severity) or to a lower stage/severity of disease compared to screening.
 - If recurrence has not occurred in a patient, the date of last disease assessment will be used as the timepoint for censoring.
 - The analysis will be repeated in an exploratory manner where recurrence is defined as only those recurrences to the same extent of disease (or greater) as screening.

- Time To Progression, defined as the time from randomization to progression.
 - Progression is defined as an increase in T stage from CIS or Ta (at screening) to T1 (lamina propria invasion), development of T2 or greater or lymph node (N+) disease or distant metastasis (M1), or an increase in grade from low to high per the IBCG recommendations..
 - If progression has not occurred in a patient, the date of last disease assessment will be used as the timepoint for censoring.

- Disease-Free Survival, defined as the time from randomization to recurrence or progression.
 - If a patient has recurred or progressed, then the first date the recurrence or progression has occurred will be used as the timepoint for the event.
 - If a patient has neither recurred nor progressed, then the date of last disease assessment will be used as the timepoint for censoring.

- Overall Survival, defined as the the time from randomization to death.
 - If a patient is still alive, then the patient will be censored on the date of most recent date known alive.
 - If a patient is lost to follow up, then the patient will be censored on the date last known alive.

- Time to cystectomy, defined as the time from randomization to cystectomy.
 - If a patient has not undergone cystectomy, the patient will be censored on the date of last disease assessment.

- Burden of repeat TURBT, defined as the proportion of patients with no repeat TURBT vs 1 TURBT vs 2 TURBT vs 3 TURBT etc within 12 months since randomization (ie day 366 or earlier), within 18 months since randomization (ie day 548 or earlier) and within 24 months since randomization (ie day 731 or earlier).

For time to recurrence, time to progression, disease-free survival and overall survival, the Kaplan-Meier estimates on the proportion of patients free from the event of interest at 3, 6, 9, 12, 18 and 24 months from randomization will be presented.

For time to cystectomy, the Kaplan-Meier estimates on the proportion of patients with cystectomy at 12, 18 and 24 months from randomization will be presented. In addition, the time to cystectomy from original TURBT will be analysed in a similar way, and the data will be presented as sensitivity analysis.

For intensity of repeat TURBT, the same analysis will be repeated using the 12, 18 and 24 months since original TURBT, as sensitivity analysis.

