#### Phase 2:

In Phase 2, the primary endpoint (proportion of patients alive and disease free at one year) between the two experimental groups and the control will be compared using Fisher's exact test and presented as odds ratios (OR) with 95% confidence intervals (CI) relative to the control group. For the statistical comparisons on the primary endpoint between the two experimental and control groups, there will be no adjustment for multiplicity. ORs will be generated with a simple logistic regression model with one year disease-free survival as the dependent variable and group as the sole independent variable (low dose and high dose vesigenurtacel-L vs. control). If the analysis of the primary endpoint does not suggest any dose response effect between the two vaccine arms, an exploratory analysis will be conducted where the two vaccine arms will be pooled and compared to the control arm for the primary endpoint (proportion of patients alive and disease-free at one year). The outcome will be presented as OR with 95% CI relative to the control group.

Efficacy comparisons between the monotherapy arm and any of the randomized arms will remain exploratory. However, safety and point estimates with appropriate measures of variance (SD, 95% CI) for the efficacy parameters for the fourth arm will be estimated.

The binary secondary endpoints will be presented as OR with appropriate 95% CI.

DFS will also be evaluated as a time to event endpoint, defined as disease recurrence or progression or death from any cause. For time to event endpoints, which will also include OS, time to cystectomy, and burden of repeat TURBT, survival curves will be generated by the method of Kaplan-Meier and compared with the log-rank test. In an exploratory analysis, the weighted log rank test will also be used. The weighted log rank preserves the statistical power that is lost due to the lag time effect in efficacy with immunotherapeutic agents.

Exploratory clinical and laboratory endpoints will be summarized descriptively by time point of collection. Statistical testing and CI will be provided as an aid in reviewing the collected data. A log10 transformation may be used as appropriate in order to determine 95% CI based on a t-test for the log-concentrations, and the bounds will be transformed back to the original scale for presentation purposes. Homogeneity between

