##### **12.5.2.3 Disease-Free Survival**

Defined as time from randomization to recurrence or progression

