##### **12.5.2.4 Overall disease-free survival**

Overall DFS is defined as the interval between the date of disease recurrence, progression, or death (whichever occurs first) and the date of randomization/treatment assignment (Arm 4) for patients without CIS. For patients with CIS at screening who have persistent disease at 6 months, the date of disease persistence will be defined as the date of randomization/treatment assignment (Arm 4) (i.e. DFS = zero).

Patients with CIS at screening who are disease-free by 6 months will have their overall DFS interval calculated between the date of disease recurrence, progression, or death (whichever occurs first) and the earliest date that the patient was determined to be disease-free. Patients will be censored at the last time of contact if recurrence, progression, or death has not been confirmed at the time of the analysis. Overall DFS will be analyzed using a log-rank test with a term for treatment assignment. In addition, Kaplan-Meier curves will be produced separately for each treatment group. The weighted log rank test will also be applied in an exploratory manner.

In a supporting analysis, a simple Cox proportional hazards model with treatment group as the sole independent variable will be built in order to estimate the hazard rate (HR) and 95%CI for overall DFS between the low and high dose vesigenurtacel-L groups relative to the control. A HR of less than one will provide initial evidence of a favorable outcome with vesigenurtacel-L. These analyses will be completed for the ITT and Per-Protocol populations.

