- Proportion of patients with progressive disease at 3, 6, 12, 18, and 24 months from randomization. Progressive disease is defined as an increase in T stage from TIS or Ta (at screening) to T1 (lamina propria invasion), development of T2 or greater or lymph node (N+) disease or distant metastasis (M1), or an increase in grade from low to high per the IBCG recommendations.
- Disease-Free survival at 3, 6, 18, and 24 months from randomization. A patient is considered as disease-free at a timepoint if the disease has not recurred nor progressed, and the patient is still alive.
- Overall Disease free survival (DFS): DFS is the time from randomization until the day of disease recurrence or progression
- Overall survival (OS): OS is the time from randomization until the day of death by any cause or censoring
- Proportion of patients undergoing a repeat TURBT by 12 months and by 24 months from randomization
- Proportion of patients undergoing cystectomy by 12 months and by 24 months from randomization
- Immunological response (IR): Peripheral blood immunological response via intracellular cytokine staining (ICS) by ELISPOT of on CD8+ cells following HS-410 vaccination will also be evaluated

Phase 2 only:

- Safety of the combination of vesigenurtacel-L and BCG
- Safety of high dose vesigenurtacel-L monotherapy

Exploratory Endpoints

In patients completing at least 6 weekly doses of study medication, the following exploratory endpoints will be evaluated:

- Immunologic response of PBMCs (analysis of surface markers, CD3, CD4, CD8, degranulation) and stimulation analysis via ICS of IFN- γ , IL-2, TNF α and perforin.
- Total PBMC counts by flow cytometry, including lymphocyte subsets (B cells, helper T-cells, cytotoxic T-cells, NK cells and T-reg)

- Evaluation of tumour tissue obtained from pre-treatment resection for antigen expression by immunohistochemical analysis
- Evaluation of tumour tissue obtained from repeat biopsy, if clinically indicated, for presence of infiltrating T-lymphocytes
- T cell receptor sequencing of peripheral blood T cells before and during the course of treatment
- Immune cell infiltration and inflammatory cytokine levels in urine (phase 2 only)

Safety Endpoints

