3.5 Study Variables

In general, the schedules of assessments (SOA) are divided into an induction and maintenance phase.

In the phase 1 component of the study, the induction phase will consist of 6 weekly vaccine doses, a one week drug free period and then followed by 6 more weekly doses. The maintenance phase will then consist of monthly treatments for 3 doses for up to a total of 15 doses, unless the criteria for treatment discontinuation are met.

In the phase 2 component of the study, the induction phase will consist of 6 weekly HS-410 (or placebo) doses in combination with 6 doses of BCG, followed by 6 weeks of HS-410 or placebo monotherapy with a vaccine holiday on Week 13 to allow for disease assessment. This will be followed by a maintenance phase consisting of 3 courses of three once-weekly injections in combination with intravesical maintenance BCG for a total of 21 doses, unless the criteria for treatment discontinuation are met. Additional maintenance therapy will be at the discretion of the treating physician.

Current Schedule of Assessments for each study are contained in the study protocol.

Study Day and Visit Windows

Patients' time on study will be determined in Study Days. Study Day 1 will be defined as the first day of dosing. Positive study days will count forward from Study Day 1. Study Day -1 will be the day before Study Day 1, and all subsequent negative study days will be measured backward from Study Day -1. There will be no Study Day 0.

A value obtained on Study Day 1 before administration of study treatment will be considered the baseline value. If a value is not available on Study Day 1, the last available value collected prior to the first dose of study drug will be used as the baseline value. The study date and corresponding study visit will be captured on each case report form (CRF) from which study day will be calculated.

Study Day will be used in the analysis of safety data and efficacy analysis. The protocol allows a 3-day window between randomization and first dose. All efficacy analyses on time-to-event endpoints will consider the date of randomization as Day 1.

4 Sample Size

Phase 1

Phase 1 is designed to provide some indication of safety and tolerability of the low dose of HS-410 as a monotherapy. A sample size of 10 patients in the monotherapy setting is deemed suitable for an assessment of safety.

Phase 2

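### The SAP's time-to-event overall DFS censors recurrence-free deaths, against protocol 12.1 and 12.5.2.4 and the SAP's own landmark definition; protocol 12.5.2.3 omits death too

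*SAP*

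**What the plan says.** **SAP.** Section 2.1 lists overall DFS as a secondary endpoint: "DFS is the time from randomization until the day of disease recurrence or progression". Section 7.2 repeats this event list under Disease-Free Survival and gives the censoring rule: "If a patient has neither recurred nor progressed, then the date of last disease assessment will be used as the timepoint for censoring". Death appears in neither place. For DFS at 3, 6, 18 and 24 months, however, section 2.1 says: "A patient is considered as disease-free at a timepoint if the disease has not recurred nor progressed, and the patient is still alive". Section 7.2 then reports, for DFS among other endpoints, "the Kaplan-Meier estimates on the proportion of patients free from the event of interest at 3, 6, 9, 12, 18 and 24 months". On the time origin, section 3.5 says: "All efficacy analyses on time-to-event endpoints will consider the date of randomization as Day 1".

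**Protocol.** Section 12.1 (Phase 2) says: "DFS will also be evaluated as a time to event endpoint, defined as disease recurrence or progression or death from any cause". Section 12.5.2.4, headed Overall disease-free survival, also counts death. Section 12.5.2.3, headed Disease-Free Survival, does not: "Defined as time from randomization to recurrence or progression". Section 12.5.2.4 adds rules for CIS. It begins "For patients with CIS at screening who have persistent disease at 6 months, the date of disease persistence will be defined" and sets that date to randomization (treatment assignment in Arm 4), so DFS is zero. CIS patients who clear by 6 months start their clock at the first disease-free date. Event-free patients are censored at last contact.

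**The concern.** Overall DFS is a named secondary endpoint with Kaplan-Meier curves, landmark proportions and a Cox estimate. Two programmers, one working from the SAP and one from protocol 12.5.2.4, would build different event flags. The SAP version treats a patient who died free of recurrence as if that patient could still recur later, and spreads the lost follow-up over the patients still at risk. From that death onwards the curve lies above the one the protocol defines. The SAP would also report two figures under the name DFS for the same month, one requiring survival and one ignoring it. Any effect on the comparison between arms depends on where the deaths fall, which cannot be known in advance.

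**Working it through.** **1. Texts side by side: is death a DFS event?**

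- SAP 2.1, overall DFS: no.
- SAP 7.2, DFS: no; such patients are censored at last disease assessment.
- SAP 2.1, DFS at 3, 6, 18 and 24 months: yes, the patient must be alive.
- SAP 2.1, primary 1-year DFS: yes, the patient must be alive.
- Protocol 12.1: yes.
- Protocol 12.5.2.3, DFS: no.
- Protocol 12.5.2.4, overall DFS: yes.

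So the SAP's time-to-event definition matches protocol 12.5.2.3 but carries the label of 12.5.2.4.

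**2. The plan's own figure.** The stated 80% power (60% against 90%, 23 evaluable per arm, one-sided 0.10, Fisher's exact test) reproduces at 80.8% by exact enumeration. It belongs to the primary test, does not use the time-to-event variable, and is unchanged by this point.

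**3. Size of the death effect.** From the documents: 25 patients per arm, 60% control DFS at one year (10 failures), and assessments at Weeks 13, 25, 37 and 49, taken here as months 3, 6, 9 and 12. Assumed: failures of 3, 3, 2 and 2 at those months, with the other 15 patients followed to month 24.

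- All failures counted: 15/25 = 60.0% at 12 months.
- One month-9 failure is instead a death at month 8, last assessed at month 6. Protocol 12.5.2.4: still 15/25 = 60.0%. SAP: the patient leaves the risk set after month 6, giving 19/25 × 17/18 × 15/17 = 19/25 × 15/18 = 63.3%.
- Both month-9 failures are such deaths. SAP: 19/25 × 15/17 = 67.1%.

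With k failures by month 6, the SAP value is (25−k)/25 × 15/(24−k) for one death and (25−k)/25 × 15/(23−k) for two. For k = 4, 5 and 6 this gives 63.0%, 63.2% and 63.3% for one death, and 66.3%, 66.7% and 67.1% for two.

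A second view assumes independent one-year mortality of 2%, 5% or 8%. A no-death DFS of 60% becomes 60 × 0.98 = 58.8%, 60 × 0.95 = 57.0% or 60 × 0.92 = 55.2% once death counts. A no-death DFS of 90% becomes 88.2%, 85.5% or 82.8%.

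**4. The CIS and clock differences, same example.**

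- *Persistent CIS, for 1 or 2 of the month-6 failures.* Coded as recurrence at Week 13 (84 days after Day 1), no reported landmark differs from dating at randomization. Dated at Week 25, only the 3-month value moves: 22/25 = 88%, against 21/25 = 84% or 20/25 = 80%. The 12-month value is 60% in each case.
- *Time origin.* A CIS patient who recurs at Week 49 (day 337) has 337 − 1 = 336 days on the SAP clock. On the protocol clock it is 337 − 85 = 252 days if clear at Week 13, or 337 − 169 = 168 days if clear at Week 25. If both month-12 failures were Week-25 clearers, 6-month DFS would be 19/25 = 76% (SAP) or 17/25 = 68% (protocol). The 12-month value is 60% on both.

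**The case against.** The SAP did not invent its definition. Its Disease-Free Survival entry follows protocol 12.5.2.3 closely, and protocol 12.1 leaves details of the methods to the SAP. That stands to this extent: the protocol contradicts itself and must be corrected too. It does not clear the SAP, which attaches the no-death definition to overall DFS and contradicts its own landmark definition.

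One or two recurrence-free deaths in 25 patients within a year is an assumption with no basis in the documents. SAP 5.5 calls the trial exploratory and reports secondary endpoints as estimates with 95% confidence intervals. Both points are fair. They limit the consequence to a biased and ambiguous secondary estimate.

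A reader might go further and call the SAP wrong on CIS dating, time origin and censoring date as well. The documents do not support that:

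- SAP 7.2 uses the first date of recurrence. For CIS seen at Week 13 and still present at Week 25, coding it as recurrence gives Week 13, and no reported landmark moves. Twelve-month values of 64% or 68% would arise only if visible CIS were never coded as an event.
- A randomization origin is defensible for comparing randomized arms; the protocol's alternative starts at a post-randomization event.
- Censoring at last assessment is defensible for an event found at visits. Protocol 6.3 schedules cystoscopy at each long-term follow-up visit for patients who finished treatment or stopped for reasons other than disease, so the two censoring dates will often coincide.

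**Conclusion.** The point holds for death and should be corrected. As written, the SAP's time-to-event DFS censors recurrence-free deaths, against protocol 12.1 and 12.5.2.4 and against the SAP's own alive-at-landmark definition. Protocol 12.5.2.3 shares the omission. In the example the 12-month estimate is about 3 points too high with one such death in 25 patients and about 7 points too high with two. The number and timing of deaths are assumed; with no such deaths the two definitions agree on this item.

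A reader might infer that the primary result is compromised or that the vaccine arms are favoured. Neither follows. The primary endpoint in SAP 2.1 requires the patient to be alive, so the Fisher test is unaffected if the rules in 7.1 are read with it, and the direction of any between-arm effect depends on which arm has the deaths. The CIS, time-origin and censoring differences are real mismatches to reconcile, but neither document's choice is shown to be the wrong one.

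**What to change.** **Main change.** In SAP 2.1 and 7.2, make death from any cause a DFS event, restrict the censoring rule to patients alive without an event, and base the Kaplan-Meier landmarks on that variable. Align protocol 12.5.2.3 with 12.1 and 12.5.2.4.

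**Minor reconciliation.**

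1. State in the SAP how CIS persisting at 6 months is dated; protocol 10.1 and 12.5.2.4 date it to randomization.
2. State in both documents one time origin for CIS patients who clear by 6 months, and one censoring date for event-free patients.
3. In SAP 7.1, restate that death and progression are failures, as SAP 2.1 already implies. Say explicitly whether persistent CIS counts as a recurrence for the primary endpoint, since neither SAP 2.1 nor protocol 12.5.1 lists it. That would be a decision about the endpoint, not a restatement.
4. The opening of SAP section 7 ranks Ta below TIS, and protocol 12.5.2.2 defines progression as a move to a greater stage. Together these imply that new CIS after high-grade Ta is progression. The progression lists in protocol 10.1 and SAP 7.2 do not include it, so reconcile them.

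**Cost.** Wording in the SAP and in a few protocol subsections. Survival and disease assessments are already collected. The downside is that reported DFS may be a few points lower.

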All patients in both the Phase 1 and Phase 2 portions of the study will have a cystoscopy and cytology and, if clinically indicated, a biopsy performed approximately every 3 months for 2 years then every 6 months for up to a year, study termination, disease progression, or recurrence requiring treatment discontinuation, whichever occurs first. Patients with evidence of disease at an assessment may continue on treatment if judged by the investigator to be in the patient's best interest (e.g. would normally receive another course of BCG therapy as standard of care (SOC)). Upon discontinuation of study treatment, additional treatment will be at the discretion of the treating physician per SOC. While treatment may continue in the presence of evidence of disease, statistical analysis of disease-free status will still follow strict definitions as defined in section 10.1 Evaluation of Disease.

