### 6.3 Long-term Follow-up Visits

All patients will be followed for the procedures listed below every 3 months from the date of the previous visit for 2 years then every 6 months from the date of the previous visit for a year or until study termination, whichever occurs first:

- Survival
- New anticancer treatments initiated after disease recurrence
- TURBT or fulguration procedures
- Cystectomy

In addition patients who have completed all study treatments or have discontinued study product dosing due to reason other than disease recurrence/progression will have the following procedures performed at each long-term follow-up visit:

- Cystoscopy/Cytology; biopsy if area suspicious for disease recurrence is identified at discretion of investigator (*Note: patients who have a biopsy performed will provide at least 4, non-stained, 10 micron sections for TCR sequencing and analysis of infiltrating T-cells.*) *If slides are not available, FFPE tissue (≥50 microns) is also acceptable.*

If a patient has recurrent/progressive disease and discontinues study treatment, the above disease assessment procedures will be discontinued, and subsequent long-term follow-up visits may be conducted via phone visit.

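### Time to cystectomy is censored at the last disease assessment although cystectomy is tracked beyond it, which biases the Kaplan-Meier cystectomy rate upward, mainly at 18 and 24 months

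*SAP*

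**What the plan says.** SAP section 7.2 defines time to cystectomy from randomization and gives one censoring rule: "If a patient has not undergone cystectomy, the patient will be censored on the date of last disease assessment". Further down it names what it will report: "For time to cystectomy, the Kaplan-Meier estimates on the proportion of patients with cystectomy at 12, 18 and 24 months from randomization". The analysis is repeated with the original TURBT as time origin. Protocol section 12.5.2.7 defines the endpoint without a censoring rule, and neither document gives a different one.

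Protocol section 6.3 sets up two streams of follow-up:

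- Survival, new anticancer treatment, TURBT or fulguration, and cystectomy: "All patients will be followed for the procedures listed below every 3 months from the date of the previous visit". This quarterly contact lasts two years, and half-yearly contact follows in the third.
- Cystoscopy and cytology, which can end earlier: "If a patient has recurrent/progressive disease and discontinues study treatment, the above disease assessment procedures will be discontinued". Later contacts with these patients are allowed by telephone.

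Recurrence alone does not end assessments, because Protocol section 3.1 leaves room to stay on treatment where that serves the patient: "Patients with evidence of disease at an assessment may continue on treatment if judged by the investigator". Progressive disease, by contrast, is on the mandatory treatment-discontinuation list in Protocol section 7.2.1.

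For overall survival, the same SAP section uses contact dates: "If a patient is lost to follow up, then the patient will be censored on the date last known alive".

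**The concern.** Censoring at the last disease assessment suits recurrence, progression and DFS, because those events are only seen at an assessment. Cystectomy is not like that. It is a surgical event recorded at every long-term contact, whether or not cystoscopy is still being done.

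Consider two patients who recur at month 6 and stop study treatment. One has a cystectomy at month 16 and is an event at month 16. The other is confirmed by phone to be cystectomy-free through month 24, but is censored at month 6. Whether a patient stays in the risk set between months 6 and 16 thus depends on what happens later. This is outcome-dependent censoring, and it falls on the patients most likely to need a cystectomy.

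At stake are the reported cystectomy proportions. If the stopping share and the post-recurrence cystectomy risk are similar across arms, the arm with more recurrences is inflated more, and the difference between arms is exaggerated.

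**Working it through.** The documents state no cystectomy rate, so there is no planned figure to reproduce. The check has three parts.

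**1. Direction.** The Kaplan-Meier proportion with cystectomy by time t is 1 − ∏(1 − d_j/n_j) over event times up to t. Event times and counts d_j are the same whether non-events are censored at the last assessment or at the last cystectomy contact. The SAP rule can only make the risk sets n_j smaller. Every factor is then equal or lower, so the estimated proportion is equal or higher, and no assumption about rates is needed. In 5,000 simulated arms of 25, the SAP estimate was never below the contact-based one. With no treatment stops the two coincide.

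**2. Worked example, 25 patients.** Thirteen recur and stop treatment, at months 3, 3, 6, 6, 6, 9, 9, 12, 12, 12, 18, 18 and 24. Three of them (recurring at months 6, 9 and 12) have cystectomies at months 10, 16 and 22. All are followed for cystectomy to month 36.

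- Contact-based censoring: 1/25, 2/25, 3/25 = 4.0%, 8.0%, 12.0% at 12, 18 and 24 months.
- SAP rule, month 10: five non-events were already censored (months 3, 3, 6, 6, 9), so 20 are at risk and 1/20 = 5.0%.
- Month 16: one event and two more censored (12, 12), so 17 are at risk; 1 − 0.95 × 16/17 = 10.6%.
- Month 22: one event and two more censored (18, 18), so 14 are at risk; 1 − 0.8941 × 13/14 = 17.0%.

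**3. Expected size.** Monte Carlo, 400,000 patients per scenario.

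- From the documents: one-year DFS of 60% (control) and 90% (experimental) from Protocol section 12.6.2; assessments 3-monthly to month 24, then 6-monthly to month 36.
- Assumed: exponential recurrence, with monthly hazard −ln(DFS)/12; cystectomy only after a detected recurrence, with a constant hazard of 15% per year (range 10% to 25%); 25%, 50% or 100% of recurring patients stop assessments; complete cystectomy contact to month 36; no deaths.

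Two readings of Protocol section 6.3 were run: a recurrence at any time can end assessments, or only one detected by month 12, because dosing ends at Week 52.

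Results at 60% DFS and 15% per year:

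| Time point | True | 25% stop | 50% stop | 100% stop (upper bound) |
|---|---|---|---|---|
| 24 months, any recurrence | 9.7% | 10.5% | 11.5% | 14.4% |
| 24 months, recurrence by month 12 only | 9.7% | 10.4% | 11.1% | 12.9% |
| 18 months, any recurrence | 5.8% | 6.2% | 6.5% | 7.7% |
| 12 months, bias in points | – | +0.1 | +0.2 | +0.5 |

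Repeat runs agree to about 0.1 to 0.2 points.

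- Cystectomy risk of 10% to 25% per year, half stopping: the 24-month bias is 1.4 to 2.2 points (any recurrence) or about 1.1 to 1.6 points (by month 12 only).
- 90% DFS: the 24-month bias is at most about 0.3 points.
- Difference between a 60% and a 90% DFS arm at 24 months, half stopping in both, 15% per year: from about 7.2 to about 8.8 points (any recurrence), or from about 7.3 to about 8.6 (by month 12 only).

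For scale, the 95% half-width at a 10% rate with 25 patients is 1.96 × √(0.1 × 0.9/25) = 11.8 points.

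**The case against.** The strongest case on the other side concerns weight rather than mechanism.

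- **Which recurrences count.** Assessments end only for patients who recur or progress and also discontinue treatment, and Protocol section 6.3 keeps cystoscopy for those who have completed all study treatment. A patient who recurs after Week 52 has no treatment left to stop. This stands, and the by-month-12 figures are the safer reading. They lower the 24-month bias by a few tenths of a point when up to half stop, and by about 1.5 points in the all-stop bound. Protocol section 3.1 also ends cystoscopy at progression, so late events are not wholly excluded.
- **The size is assumed.** Neither the stopping share nor the cystectomy risk is in the documents, and with no stops the bias is zero. This also stands; the direction does not depend on those inputs.
- **Small practical effect.** In an arm of 25, 1.8 points is less than half a patient, well inside sampling error. The endpoint is secondary, SAP section 5.5 limits p-values to the primary analysis, and the 12-month estimate is barely touched.
- **A crude proportion would avoid it.** The endpoint is named as a proportion by 12 and 24 months, and the Protocol plans odds ratios for binary secondary endpoints. But the only cystectomy analysis detailed in SAP section 7.2 is the Kaplan-Meier one.
- **Undefined term.** The SAP does not define the last disease assessment. If later TURBT or fulguration records counted as assessments, the gap would shrink, but nothing in the text says they do.

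None of this gives a reason to keep the rule.

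**Conclusion.** The concern holds. As written, the rule can only raise the Kaplan-Meier cystectomy proportion, and does so whenever an observed non-event is removed before a later cystectomy. This rests on the natural reading that cystectomies after the last assessment are counted at their own date; it would reverse only if they were ignored, which the SAP does not say.

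Under the assumptions above, with half of recurring patients stopping and 60% one-year DFS, the 24-month excess is roughly 1 to 2 points on a true rate of about 10%. The excess is smaller at 18 months, slight at 12 months, and close to nothing in an arm with 90% DFS. The primary one-year DFS analysis is unaffected. The correction should be made because the bias is systematic, would not shrink with more patients, and recurs in the repeat analysis from the original TURBT.

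**What to change.** In SAP section 7.2, censor patients without cystectomy at the latest date on which their cystectomy status was ascertained: the last disease assessment or the last long-term follow-up contact (visit or phone), whichever is later. Apply the same rule to the sensitivity analysis from the original TURBT. This matches the contact-based censoring already used for overall survival in that section. Treating death before cystectomy as a competing event is optional, but the SAP should say how such deaths are handled.

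The cost is one sentence of SAP text and one change of censoring date in the program. No new data are needed, because Protocol section 6.3 already collects cystectomy status at each long-term follow-up contact.
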